### Procedure:

#### Visit 1 (Screening and Initial Treatment Visit)

- Verify that subject is qualified to participate in the study.
- Ask subject to give personal information, such as name, date of birth, race and ethnicity.
- Review medical and dermatology (skin) history, including history of previous treatments to area being treated.
- Review past and current medications and skin care products.
- See how tall subject is and how much subject weighs
- If subject is a woman and can have children, urine will be tested to see if subject is pregnant. The study doctor or study staff will tell subject if pregnancy test results are positive. The results of the pregnancy testing must be negative in order for subject to be in the study.
- Supply patient with topical cysteamine cream and review instructions for its use
- Identify and examine the area (i.e, side) of face to which the Diode 1927 nm laser will be used (mapping)
- Take photos of face
- Perform grading of melasma
- Perform treatment according to guidelines stated in protocol
- Schedule the next study visit

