#### Visit 2 and 3 (Week 4 and 8)

- Assess side-effects of the treatment at initial visit
- See how tall subject is and how much subject weighs
- Perform treatment according to guidelines stated in protocol
- Schedule the next study visit
- Take photos of face

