The primary objective of our study is to determine the efficacy of combined topical cysteamine cream with a 1927 diode non-ablative laser (Clear + Brilliant Permea®; Solta Medical, Inc.), compared to topical cysteamine alone in the treatment of melasma. This efficacy will be assessed using modified Melasma Area and Severity Index (mMASI) scores, a validated physician assessment tool, at baseline and at follow up visits at week 4, 8 and 12 as well as Investigator Global Assessments. Secondary objectives also include an assessment of patient satisfaction which will be evaluated via patient questionnaires distributed to patients at baseline and at week 12. In addition, impact on quality of life will also be assessed utilizing the melasma quality of life scale (MELASQoL) questionnaire which will be administered to patients at baseline and at week 12.

Multiple studies have demonstrated the efficacy of topical cysteamine in the treatment of melasma. Mansouri et al. conducted a double-blind, randomized, controlled clinical study, which included 50 melasma patients, and demonstrated significant efficacy of topical cysteamine in the treatment of melasma. One comparative trial demonstrated that topical 5% cysteamine, though safe and well-tolerated, was less effective than topical 4% hydroquinone in the treatment of facial melasma; however, a later published response indicated that the concentration of cysteamine may have been less than the reported 5%. A single-blind, randomized comparative trial of 54 melasma patients found no statistically significant difference in the efficacy of topical cysteamine compared to topical tranexamic acid; however, cysteamine was better tolerated amongst the patients. Finally, Karrabi et al. also found that cysteamine 5% cream showed greater efficacy than the gold standard, modified Kligman's formula, in their randomized, double-blind trial of 50 patients with epidermal melasma.

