We hypothesize that addition of 1927-nm fractional low-powered diode laser therapy to topical 5% cysteamine will result in significantly greater improvement in both the clinical appearance of melasma as well as patient satisfaction, compared to topical cysteamine alone. Specifically, we hypothesize:

- 1) Patients will experience improvement in their melasma on both treated sides, with greater improvement noted with combined topical and 1927-nm fractional low-powered diode laser treatment noted on their mMASI scores at weeks 4, 8 and 12.
- 2) Patients will report improvement in satisfaction on patient questionnaires on both treated sides, however there will be greater change in satisfaction noted with combined topical and 1927-nm fractional low-powered diode laser treatment at week 12 compared to baseline (week 0)

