**Objectives:**

- A. To evaluate the efficacy of the Clear & Brilliant Permea laser system in combination with topical cysteamine
  - a. To assess for improvement of melasma after completion of three treatments as determined by the treating clinician and objective measures
  - b. To evaluate subject's satisfaction with melasma treatment and assessment of improvement after three treatments
  - c. To evaluate the length of treatment.
- B. To evaluate the safety of melasma treatment in all skin types using the Clear & Brilliant Permea laser in combination with topical cysteamine
  - a. To evaluate the immediate response to treatment
  - b. To evaluate the subject's assessment of comfort associated with treatments
  - c. To determine the rate of adverse events for the treatment group as a whole

**Study Design:** Single Center, Prospective, With Before-After Analysis

**Study population:** Twenty healthy male or female patients, 18-74 years of age, of all skin types with melasma on the face that wish to be treated. Each subject will receive topical cysteamine cream which they will be instructed to use once a day at home. In addition, one side of the face will be randomly selected for treatment with laser. Patients will receive three monthly treatments, at 4-6 week intervals, on the selected side of the face with the Clear & Brilliant Permea laser. The treatment duration including pre and post treatment procedures is estimated to be 90 minutes per subject. Subjects will return for a follow-up visit 3 months after the initial treatment for a total of four visits. The treatment plan will be the same regardless of the subject's skin type. Four passes, at high setting will be performed.

During the first and fourth visit, the areas of treatment will be photographed with a digital camera under controlled conditions. Subject improvement will be assessed via investigator and subject grading at visit 1 and 4. Improvement in melasma will be assessed by blinded evaluators who will review pre and post treatment photographs taken with VISIA® Skin Analysis System for facial imaging (Canfield Scientific Inc) from visit 1 and 4. Side effects (including pain, redness, dryness, and hyperpigmentation) will be assessed and recorded at visits 2, 3, 4.

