**Photographs:**

Photographs will be taken at each visit prior to treatment and at follow-up visit 4, to evaluate healing time, clinical improvement of melasma, as well as any side effects. Photographs will be taken using the VISIA® Skin Analysis System for facial imaging (Canfield Scientific Inc). This device ensures face position, lighting, photographer, and camera settings are standardized.

Subjects will be asked to remove all skincare products applied to the facial area prior to treatment with a gentle cleanser and clean towel. Participants will be instructed to sit down & place their face in the holder of the VISIA®. This camera will take 3 pictures of the face, including the left, right, and front facial areas. Study staff may need to adjust the height of the chair and or face holding piece inside the VISIA® for subject comfort.

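### The primary objective and hypothesis 1 need mMASI at weeks 4, 8 and 12, but the visit schedule grades melasma only at visit 1 and visit 4 (week 12), and the endpoint section gives a third timing

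*Protocol*

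**What the plan says.** **What is to be shown.** In the Background section of the protocol, the primary objective has efficacy assessed by mMASI "at baseline and at follow up visits at week 4, 8 and 12". Hypothesis 1, in the same part of the document, expects the greater benefit of the combination to be "noted on their mMASI scores at weeks 4, 8 and 12".

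**What is scheduled.** The list for visit 1 includes "Perform grading of melasma", and the list for visit 4 (week 12) repeats that item. The list for visits 2 and 3 (weeks 4 and 8) has side effects, height and weight, treatment, scheduling and "Take photos of face", but no grading. The study population text under Objectives says "Subject improvement will be assessed via investigator and subject grading at visit 1 and 4", and has the blinded evaluators review photographs from those two visits. The Clinical Evaluations section refers to the visit procedure summary for what is done when.

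**The endpoint section.** Criteria of Evaluation dates the in-person mMASI change from baseline (visit 1) to week 4. It places the blinded photographic comparison and GAIS at visit 4, and the quartile score at week 12.

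**Photographs.** The Photographs section says "Photographs will be taken at each visit prior to treatment and at follow-up visit 4", which agrees with the visit lists. The study population text says "During the first and fourth visit, the areas of treatment will be photographed with a digital camera under controlled conditions" and mentions no other visit.

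**The concern.** A time point named in the primary objective and in a numbered hypothesis should have a matching assessment in the schedule. Here weeks 4 and 8 do not. Sites work from the visit lists, so the likely outcome is that no mMASI is recorded at either visit. No later analysis document can restore an in-person score that was never taken.

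Two things are at stake. First, hypothesis 1 cannot be tested as written at two of its three time points. Second, all scheduled post-baseline efficacy measures fall at one visit, so a patient who leaves before week 12 contributes nothing to the side comparison. It also could not be seen from scheduled scores whether those who left were doing worse on the lasered side.

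**Working it through.** **1. The timing statements side by side**

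| Place in protocol | mMASI or melasma grading | Photographs |
|---|---|---|
| Background, primary objective | baseline, weeks 4, 8, 12 | – |
| Hypothesis 1 | weeks 4, 8, 12 | – |
| Visit lists | visits 1 and 4 | visits 1, 2, 3, 4 |
| Study population text under Objectives | visits 1 and 4 | visits 1 and 4 |
| Photographs section | – | every visit |
| Criteria of Evaluation, in person | baseline and week 4 | – |
| Criteria of Evaluation, blinded readers | baseline and visit 4 | – |

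By the visit lists, week 4 is visit 2 and week 12 is visit 4. If the in-person endpoint is a slip for visit 4, weeks 4 and 8 both lack scores. If it is literal, week 4 has an endpoint but no grading item in the visit list, and week 8 still has no score anywhere outside the Background section.

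**2. A patient who leaves after week 8**

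Laser is given at visits 1, 2 and 3, so this patient has had all three treatments. Under the visit lists there are also three sets of images. Investigator mMASI, blinded mMASI, quartile score, GAIS and the post-treatment questionnaire are all tied to visit 4 or week 12, so the number of scheduled post-baseline efficacy scores is zero.

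**3. The sample size statement**

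The Sample Size Calculation section gives 20 subjects, 80% power and a two-sided 5% level for a paired t-test (its first sentence says one-sided), with up to 25 enrolled. No effect size or SD is stated, so 20 cannot be reproduced. The standardised paired difference d can be solved for instead.

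- Exact: power from the noncentral t with n − 1 degrees of freedom and noncentrality d√n. Setting power to 0.80 at n = 20, two-sided, gives d = 0.66.
- Normal check: (1.960 + 0.842)/√20 = 0.63.
- Enrolment allowance: 20/(1 − 0.20) = 25, so 25 corresponds to 20% dropout.

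**4. Power if pairs are lost (d = 0.66, two-sided 5%)**

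| Evaluable pairs | 20 | 19 | 18 | 17 | 16 | 15 |
|---|---|---|---|---|---|---|
| Power | 0.800 | 0.777 | 0.752 | 0.725 | 0.695 | 0.663 |

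If 20 enrol and 4 stop early (4/20 = 20%), 16 pairs remain and power is about 70%. If 25 enrol and 20% are lost, 25 × 0.80 = 20 pairs remain and power is 80%. On the one-sided reading, d = 0.58 and power at 16 pairs is 0.711, a similar fall.

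**5. What interim scores would recover**

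Assume all four stop after week 8 and have a week 8 score. With N enrolled, m completers and an assumed correlation r between the week 8 and week 12 side differences, the variance of the week 12 mean is proportional to (1 − r²)/m + r²/N. Its reciprocal is the effective number of pairs. With N = 20 and m = 16:

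- r = 0.5: 0.75/16 + 0.25/20 = 0.0594, effective n 16.8, power about 72%.
- r = 0.7: 0.51/16 + 0.49/20 = 0.0564, effective n 17.7, power about 74%.
- r = 0.9: 0.19/16 + 0.81/20 = 0.0524, effective n 19.1, power about 78%.

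Power here is interpolated in the table above, for example 0.695 + 0.8 × (0.725 − 0.695) = 0.719. The correlations are assumptions; the protocol gives none. Patients who leave before week 4 gain nothing.

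**The case against.** **The formal objectives fit visit 4.** The Objectives section seeks improvement after completion of three treatments, which visit 4 grading serves. Cutting weeks 4 and 8 from the Background section would also remove the contradiction. That is fair: interim grading is one of two ways to make the document consistent. The shorter edit, however, gives up two time points of the stated hypothesis and leaves early leavers without a score.

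**Grading is not confined to visits 1 and 4 everywhere.** A reader might infer that no part of the protocol beyond the Background section asks for an interim score. Read literally, the endpoint section asks for one at week 4, and a patient reaching that visit would then have one post-baseline score. The statement about grading visits is therefore true of the visit lists and the design text, not of the whole document. This makes the conflict three-way.

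**Partial data would not be beyond use.** A reader might also infer that no sound method could use the data of those who drop out. The documents do not support that. If photographs are taken at weeks 4 and 8, they could be read for mMASI later, although the study population text puts even those photographs in doubt. How dropouts are analysed may properly be left to an SAP. Whether the scores are collected cannot.

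**The power loss may not occur.** The enrolment allowance covers 20% dropout if it is used in full. This stands, and limits the power argument to the case where enrolment stops near 20. That case is possible: the study population is given as twenty, and 25 is only a permitted maximum.

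**Conclusion.** The contradiction holds. If the visit lists are followed, two of the three time points in hypothesis 1 have no scores. If the week 4 endpoint is literal, week 8 still has none. Under the visit lists, a patient leaving after week 8 has no scheduled post-baseline efficacy score despite complete laser treatment.

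It would be wrong to infer that the trial is underpowered because of this, or that interim grading would restore full power. The fall from 80% to about 70% requires enrolment of only 20 with 4 early stoppers, and rests on a d of 0.66 that the protocol does not state. Interim scores would bring that to between 72% and 78% for assumed correlations of 0.5 to 0.9, if all four leave after week 8. The main reason to act is that the stated hypothesis and the schedule do not match, which should be settled before enrolment.

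**What to change.** - Add mMASI grading, by side and before laser, to the list for visits 2 and 3. The Clinical Evaluations section already requires scoring before treatment.
- Align the study population text and Criteria of Evaluation with the primary objective and hypothesis 1. Settle whether the in-person endpoint is meant for week 4 or visit 4, and keep week 12 as the main time point.
- Reconcile the photograph schedule: the study population text against the visit lists and the Photographs section.
- Where week 4 and week 8 photographs are taken, have the same two blinded dermatologists score them masked to visit.

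The cost is a few minutes of grading at two visits that already take place, and more image reading by the same readers. No new visit is needed. If interim scores are not wanted, the least that must change is the primary objective and hypothesis 1, which should then name week 12 only, together with the endpoint date. Early leavers would then still have no score.

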#### Visit 4 (Week 12)

- Assess side-effects of treatment
- See how tall subject is and how much subject weighs
- Take photos of face
- Perform grading of melasma
- Post-treatment questionnaire
- Evaluation of photos comparing visit 1 and 4 to be performed

**Risks and Discomforts:** Blistering, edema, erythema and local pain are typical reactions to laser treatment. A lesser possibility exists for hyperpigmentation, hypopigmentation scarring, and/or infection. These conditions may or may not resolve over time. As with any method of tissue destruction, there is a risk of infection and of scarring, which is minimized with proper wound care. Eye injury due to the use of the laser is a risk to the subject as well as the operator. The subjects may experience partial or permanent hair reduction. Risks of the topical include temporary irritation, burning or heating up sensation that resolves within 30 minutes

**Benefits:** The subjects may or may not show improvement of melasma on the treatment sites. There is no guarantee of success.

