**Intended Use of the Data:**

The expected end use of the data collected will be for the purpose of best practices in treating melasma on the face. As the purpose of the study is to evaluate the safety and efficacy of low energy diode 1927nm, follow-up photos will be examined for melasma improvement by both the investigator(s) and blinded dermatologist reviewers. A satisfaction questionnaire will be given to patients one month after the final laser treatment. Photos and the satisfaction questionnaire will be examined by the principal investigator and sponsor to determine best practices for use of low energy diode 1927nm in treating melasma in face.

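### Hypothesis 2 needs a baseline satisfaction score for each side of the face, but the visit lists schedule only a post-treatment questionnaire and no schedule says it is answered by side

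*Protocol*

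**What the plan says.** The Background section of the Protocol sets two specific hypotheses. The second concerns satisfaction. It expects that "Patients will report improvement in satisfaction on patient questionnaires on both treated sides", and then predicts "greater change in satisfaction noted with combined topical and 1927-nm fractional low-powered diode laser treatment at week 12 compared to baseline (week 0"). The contrast is therefore a difference between sides in the change from week 0 to week 12.

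Earlier in Background, the secondary objectives give timings that fit this. They name "patient satisfaction which will be evaluated via patient questionnaires distributed to patients at baseline and at week 12", and for quality of life the "melasma quality of life scale (MELASQoL) questionnaire which will be administered to patients at baseline and at week 12".

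The operational text differs:

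- The Visit 1 list covers eligibility, history, height and weight, pregnancy test, supply of cream, mapping, photographs, grading of melasma and treatment. It has no questionnaire.
- The list for Visits 2 and 3 has none either.
- The Visit 4 list has one entry, "Post-treatment questionnaire".
- Intended Use of the Data states: "A satisfaction questionnaire will be given to patients one month after the final laser treatment".
- Objective A.b concerns satisfaction once three treatments have been given. It mentions neither a baseline nor a comparison of sides.
- Criteria of Evaluation (Study Endpoints) lists neither satisfaction nor the MELASQoL.

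**The concern.** A change from baseline needs a baseline. A coordinator who works through Visit 1 item by item would hand out no questionnaire, and once the first laser session has been given and the cream started, a week 0 score cannot be obtained. No later analysis plan can restore it. What each visit collects is a matter for the protocol, so this cannot be left to the statistical analysis plan.

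The second gap is the unit of measurement. Each patient has cysteamine on both sides and laser on one. A single overall satisfaction score therefore cannot show whether the laser side did better. Hypothesis 2 speaks of both sides, but no text on scheduling or endpoints tells staff to have the questionnaire answered once per side.

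At stake is one of the two stated hypotheses in the form in which it is written, together with the baseline for the quality-of-life objective.

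**Working it through.** The protocol gives no figure for satisfaction. The sample size statement (20 subjects, 80% power) is not tied to this endpoint, so there is nothing to reproduce. The check compares what hypothesis 2 needs with what each section schedules.

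**Step 1: what hypothesis 2 needs.** Write L for the laser side and C for the side with cysteamine alone, with subscripts for weeks. For each patient the contrast is

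D = (L12 − L0) − (C12 − C0).

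This takes 2 sides × 2 time points = 4 values per patient. For 20 patients that is 4 × 20 = 80 values, of which 2 × 20 = 40 belong to week 0.

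**Step 2: what each section schedules.**

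| Place in the Protocol | Week 0 satisfaction | Week 12 satisfaction | Answered by side? | MELASQoL |
|---|---|---|---|---|
| Background, objectives text | yes | yes | not stated | week 0 and week 12 |
| Background, hypothesis 2 | yes | yes | yes | not mentioned |
| Visit 1 list | none | n/a | n/a | none |
| Visits 2 and 3 list | n/a | n/a | n/a | none |
| Visit 4 list | n/a | a post-treatment questionnaire, content not named | not stated | not named |
| Intended Use of the Data | not mentioned | yes, one month after last laser | not stated | not mentioned |
| Objective A.b | not mentioned | after three treatments | not stated | not mentioned |
| Study Endpoints | not listed | not listed | n/a | not listed |

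On the visit schedule, the last laser session is at week 8. One month later is about week 8 + 4 = 12, so Intended Use of the Data and the Visit 4 list appear to describe the same questionnaire.

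**Step 3: what is left if the visit lists are followed.** L0 and C0 are absent for every patient, so 0 of the 40 week 0 values are collected and D cannot be computed. L12 and C12 exist only if the Visit 4 questionnaire is answered by side, which no schedule states.

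**Step 4: whether another measure can stand in.** The subject grading at Visits 1 and 4 (Study population) is of improvement. The subject's GAIS rates appearance against pretreatment. Neither is a satisfaction score, and neither is stated to be by side.

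**Step 5: what can be rescued without a baseline.** Rearranging,

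D = (L12 − C12) − (L0 − C0).

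The laser side is chosen at random, so L0 − C0 has expectation zero. The paired difference at week 12, L12 − C12, then estimates the same mean difference between regimens as D does. It needs 2 values per patient, both at Visit 4, but they must be given by side.

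**The case against.** The strongest reply is that the baseline is planned. Background says so in plain terms, for satisfaction ("patient questionnaires distributed to patients at baseline and at week 12") and for the MELASQoL, and hypothesis 2 agrees with it. The visit lists are visibly incomplete in other respects. Visit 1 names neither informed consent nor the random choice of side, no list names the GAIS or the VAS pain score, and Visits 2 and 3 list no melasma grading although Background plans mMASI at weeks 4 and 8. Absence from such a list is weak evidence that something will not be done. The Clinical Evaluations section does refer evaluations to the visit procedure summary, but its text concerns the investigator's scoring, not patient questionnaires.

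This stands as far as it goes, and it rules out a stronger reading. A reader might infer that hypothesis 2 simply cannot be tested from the data to be collected. The documents do not support that: one section requires the baseline questionnaire and others omit it. Intended Use of the Data does not exclude a baseline questionnaire either, since it does not say that the later one is the only one.

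A reader might also object that the MELASQoL cannot compare the two sides of one face. The Protocol does not describe how the instrument is scored and never uses it to compare sides. The only point here is its absence from the visit lists.

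What the reply does not remove is the contradiction itself, or the missing by-side instruction, which would remain even if the timings in Background were followed.

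**Conclusion.** The point holds as an internal contradiction. Background, in its objectives text and in hypothesis 2, requires satisfaction at week 0 and week 12, with the change compared between sides. The Visit 1 list omits any questionnaire, Visit 4 and Intended Use of the Data give only a post-treatment one, and no schedule or endpoint text makes it by side.

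The size is conditional. If staff follow the visit lists, the week 0 score is missing for every patient, hypothesis 2 cannot be computed as worded, and the MELASQoL baseline is missed as well. If they follow Background, the baseline exists, but the comparison of sides still depends on an instruction that the schedule does not give. The documents do not settle which will happen.

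The consequence is limited in two ways. Satisfaction is a secondary objective and the primary mMASI comparison is unaffected. A comparison of satisfaction between sides at week 12 also survives a missed baseline, provided the Visit 4 questionnaire is answered by side. The change is still worth making before the first patient is treated, because the loss cannot be reversed afterwards.

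**What to change.** Reconcile Background, the visit lists and Intended Use of the Data in one of two ways.

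1. Keep hypothesis 2. Add to Visit 1, before the first treatment, and to Visit 4 the satisfaction questionnaire, answered separately for the left and right side, and the MELASQoL. The Visit 1 items should be ones that a patient can answer before any treatment.
2. Restate hypothesis 2 as a paired comparison of satisfaction between the two sides at week 12, and state at Visit 4 that the questionnaire is answered for each side. Random selection of the laser side supports this without a baseline. The MELASQoL still has to be added to Visits 1 and 4 if its objective is kept.

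The cost is a few lines of text and a few minutes of questionnaire time at Visit 1. The restated hypothesis alone costs only wording.
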